- p Whenever response/diagnosis is assessed in the Follow-up Period (ie, every 8 weeks [ $\pm$  28 days]). See Section 6.3 for details.
- q Day 1 ( $\pm$  14 days) of every 3rd cycle (eg, Cycles 3, 6, 9, etc) or more frequently per standard institutional practice. Not necessary for the EOT Visit if last performed within 14 days.
- r Day 1 ( $\pm$  28 days) of every 6th cycle (eg, Cycles 6, 12, 18, etc) or more frequently per standard institutional practice. Not necessary for the EOT Visit if last performed within 28 days.
- s Continuous starting after signing ICF through 28 days after the last study treatment. See Section 6.4.1 for details.
- t Including type, number of units, reasons, and date of transfusions taken  $\leq$  8 weeks prior to the start of study treatment through 28 days after the last study treatment. Thereafter, transfusions will continue to be collected until the next AML therapy after discontinuation from study treatment, death, lost to follow-up, withdrawal of consent for further data collection, or the End of Trial, whichever occurs first.
- v In addition to the frequency specified in the table, samples will also be collected if clinically indicated (eg, confirmation of CR/CRi/CRp, morphologic relapse after CR/CRi/CRp, or progression by a repeated bone marrow assessment at least 1 month later) or required for toxicity assessment. A sample of bone marrow and peripheral blood must also be sent at these time points for central pathology review.
- w Within 7 days prior to Day 1 of Cycle 2. The assessment is not required at Day 1 of Cycle 1.
- x Within 7 days prior to Day 1 of Cycle 3. The assessment is not required at Day 1 of Cycle 4.
- y Within 7 days prior to Day 1 of Cycle 5 and Day 1 of every 2nd cycle thereafter (eg, Cycles 7, 9, etc).
- z Not necessary for the EOT Visit if last performed within 28 days.
- bb A bone marrow biopsy can be collected in conjunction with an aspirate if it is standard institutional practice. A bone marrow biopsy must be collected if adequate aspirate is not attainable.
- cc A standard cytogenetic metaPhase preparation will be prepared if the bone marrow aspirate is obtained for assessing CR, morphologic relapse, or progressive disease and will be sent to the local laboratory for cytogenetic analysis.
- dd Including diary cards. See Section 7.6 for details.

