## 9. STATISTICAL CONSIDERATIONS

The sections below provide an overview of the proposed statistical considerations and analyses. The final statistical analysis methods will be documented in detail in the statistical analysis plan (SAP).

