## Appendix F: International Working Group Acute Myeloid Leukemia Response Criteria

Hematologic Response According to modified IWG Criteria for AML	
Category	Definition
Morphologic Complete Remission (CR)	Defined as less than 5% blasts in a BM aspirate sample with marrow spicules and with a count of at least 200 nucleated cells. There should be no blasts with Auer rods and absence of extramedullary disease. Plus, all the following conditions should be met: 
 
ANC <math>\geq 1 \times 10^9/L</math> (1,000/<math>\mu</math>L)
 
Platelet count <math>\geq 100 \times 10^9/L</math> (100,000/<math>\mu</math>L)
 
Independent of red cell transfusions for <math>\geq 1</math> week immediately before each response assessment
 

Morphologic Complete Remission with Incomplete Neutrophil Recovery (CRi)a	Defined as all criteria of morphologic CR except the following: 
 
ANC <math>< 1 \times 10^9/L</math> (1,000/<math>\mu</math>L)
 

Morphologic Complete Remission with Incomplete Platelet Recovery (CRp)a	Defined as all criteria of morphologic CR except the following: 
 
Platelet count <math>< 100 \times 10^9/L</math> (100,000/<math>\mu</math>L)
 

Morphologic Leukemia-free State (MLFS)	Defined as less than 5% blasts in a BM aspirate sample with marrow spicules and with a count of at least 200 nucleated cells. There should be no blasts with Auer rods and absence of extramedullary disease
Partial Remission (PR)	Defined as all hematologic criteria of morphologic CR with a $> 50\%$ decrease in the percentage of BM blasts to 5% to 25% (a blast count value of $< 5\%$ may also be considered a partial remission if Auer rods are present) b
Cytogenetic Complete Remission (CRc)	Defined as CR/CRi/CRp with a reversion to a normal karyotype in cases with an abnormal karyotype at baseline, based on evaluating $\geq 20$ metaphase cells from BM
Morphologic Relapse after CR/CRi/CRpa	Defined as one of the following conditions: 
 
Reappearance of <math>\geq 5\%</math> blasts in the BM not attributable to any other cause (eg, BM regeneration after consolidation therapy); or
 
Development of extramedullary disease
 

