Not evaluable (NE)a	Defined as without a post-treatment response assessment
Stable Disease (SD)a	Defined as failure to meet any of the above criteria and not meeting the criteria of progressive disease (see below)
Progressive Disease (PD)a	Defined as one of the following conditions: 
 
For subjects with 5 to 70% BM blasts at baseline: a <math>> 50\%</math> increase of BM blast count percentage from baseline to <math>\geq 20\%</math>; or
 
For subjects with <math>> 70\%</math> BM blasts at baseline: a doubling of absolute blast count in peripheral blood from baseline to <math>\geq 10 \times 10^9/L</math> (10,000/<math>\mu</math>L); or
 
Development of new extramedullary disease since last response assessment
 
 Progressive disease is to be confirmed by 2 consecutive response assessments separated by at least 1 month. The date of progressive disease is defined as the first date that one of three conditions listed above was met.

AML = acute myeloid leukemia; ANC = absolute neutrophil count; BM = bone marrow; IWG = International Working Group. CRh = morphologic complete remission with partial hematologic recovery: defined as less than 5% blasts in a BM aspirate sample with marrow spicules plus ANC  $> 500 \times 10^9/L$  (1,000/ $\mu$ L) & Platelet count  $> 50 \times 10^9/L$  (100,000/ $\mu$ L).

a Modification to IWG response criteria.

b If the pre-treatment bone marrow blast percentage was 50% to 100%, the percentage of blasts must decrease to a value between 5% and 25%; if the pre-treatment blast percentage was 20% to less than 49%, they must decrease by at least half to a value of more than 5%.

Notes: Deletions to the IWG response criteria are not shown.

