10.2.11. Sponsor Derived CR and CRh

Sponsor derived CR and CRh rate is defined as rate of CR and CRh based on laboratory data. CRh is defined as less than 5% blasts in a BM aspirate sample with marrow spicules plus ANC > 0.5 x 10⁹/L (1,000/ μ L) & Platelet count > 50 x 10⁹/L (100,000/ μ L).

Number and percentage of subjects with sponsor derived CR and CRh will be summarized by treatment arm. Comparisons between two treatment arms will be analyzed by Fisher's exact test.

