17.4. International Working Group Acute Myeloid Leukemia Response Criteria

Hematologic Response According to modified IWG Criteria for AML	
Category	Definition
Morphologic Complete Remission (CR)	Defined as less than 5% blasts in a BM aspirate sample with marrow spicules and with a count of at least 200 nucleated cells. There should be no blasts with Auer rods and absence of extramedullary disease. Plus, all the following conditions should be met: 
 ANC $\geq 1 \times 10^9/L$ (1,000/μL) Platelet count $\geq 100 \times 10^9/L$ (100,000/μL) Independent of red cell transfusions for ≥ 1 week immediately before each response assessment
Morphologic Complete Remission with Incomplete Neutrophil Recovery (CRi)^a	Defined as all criteria of morphologic CR except the following: 
 ANC $< 1 \times 10^9/L$ (1,000/μL)
Morphologic Complete Remission with Incomplete Platelet Recovery (CRp)^a	Defined as all criteria of morphologic CR except the following: 
 Platelet count $< 100 \times 10^9/L$ (100,000/μL)
Morphologic Leukemia-free State (MLFS)	Defined as less than 5% blasts in a BM aspirate sample with marrow spicules and with a count of at least 200 nucleated cells. There should be no blasts with Auer rods and absence of extramedullary disease
Partial Remission (PR)	Defined as all hematologic criteria of morphologic CR with a $> 50\%$ decrease in the percentage of BM blasts to 5% to 25% (a blast count value of $< 5\%$ may also be considered a partial remission if Auer rods are present) ^b
Cytogenetic Complete Remission (CRc)	Defined as CR/CRi/CRp with a reversion to a normal karyotype in cases with an abnormal karyotype at baseline, based on evaluating ≥ 20 metaphase cells from BM
Morphologic Relapse after CR/CRi/CRp^a	Defined as one of the following conditions: 
 Reappearance of $\geq 5\%$ blasts in the BM not attributable to any other cause (eg, BM regeneration after consolidation therapy); or Development of extramedullary disease
Not evaluable (NE)^a	Defined as without a post-treatment response assessment
Stable Disease (SD)^a	Defined as failure to meet any of the above criteria and not meeting the criteria of progressive disease (see below)

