Progressive Disease (PD)^a	Defined as one of the following conditions: 
 For subjects with 5 to 70% BM blasts at baseline: a $> 50\%$ increase of BM blast count percentage from baseline to $\geq 20\%$; or For subjects with $> 70\%$ BM blasts at baseline: a doubling of absolute blast count in PB from baseline to $\geq 10 \times 10^9/L$ (10,000/μL); or Development of new extramedullary disease since last response assessment 
Progressive disease is to be confirmed by 2 consecutive response assessments separated by at least 1 month. The date of progressive disease is defined as the first date that one of three conditions listed above was met.

AML = acute myeloid leukemia; ANC= absolute neutrophil count; BM= bone marrow; PB=peripheral blood;;IWG= International Working Group. CRh= morphologic complete remission with partial hematologic recovery: defined as less than 5% blasts in a BM aspirate sample with marrow spicules plus ANC $> 0.5 \times 10^9/L$ (1,000/ μ L) & Platelet count $> 50 \times 10^9/L$ (100,000/ μ L).

^a Modification to IWG response criteria.

^b If the pre-treatment BM blast percentage was 50% to 100%, the percentage of blasts must decrease to a value between 5% and 25%; if the pre-treatment blast percentage was 20% to less than 49%, they must decrease by at least half to a value of more than 5%.

Notes: Deletions to the IWG response criteria are not shown.

17.5. Hematologic Improvement According to the International Working Group for Myelodysplastic Syndromes

Hematologic Improvement According to IWG Criteria	
Hematologic improvement ^a	Response criteria (responses must last at least 8 week) ^b
Erythroid Response (HI-E) (pre-treatment, < 11 g/dL)	
 Hemoglobin increase by ≥ 1.5 g/dL Relevant Reduction in units of RBC transfusions by an absolute number of at least 4 RBC transfusions/8 week compared with the pretreatment transfusion number in the previous 8 weeks 
Note: Only RBC transfusions given for a hemoglobin of ≤ 9.0 g/dL on treatment will count in the RBC transfusion response evaluation^b

Platelet Response (HI-P) (pre-treatment, < $100 \times 10^9/L$)	
 Absolute increase of $\geq 30 \times 10^9/L$ for subjects starting with $> 20 \times 10^9/L$ platelets Increase from $< 20 \times 10^9/L$ to $> 20 \times 10^9/L$ and by at least 100%^b

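### Every CRh definition contradicts itself: the bracketed per-µL figures are the full-CR cut-offs, twice the SAP's main values, and the protocol also prints ANC > 500 x 10^9/L

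*SAP*

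**What the plan says.** CRh is defined in three places. Each gives a main value in 10^9/L and a bracketed equivalent per µL (the quotes stop just before the unit).

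- **SAP 10.2.11:** "ANC > 0.5 x 10⁹/L (1,000" and "Platelet count > 50 x 10⁹/L (100,000", together with less than 5% marrow blasts in an aspirate with spicules.
- **SAP 17.4, table footnote:** the same main values and the same brackets.
- **Protocol Appendix F, table footnote:** the same platelet statement, but the ANC threshold reads "> 500 \times 10^9/L$ (1,000".

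In the same tables, full CR requires ANC of at least 1 x 10^9/L (1,000/µL) and platelets of at least 100 x 10^9/L (100,000/µL).

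Protocol Table 2 and SAP Table 2 list the sponsor-derived CR+CRh rate as a secondary endpoint for Phase 2, and a CR/CRh endpoint for Phase 1b. SAP 10.2 and 10.2.11 compare the Phase 2 rate between arms. SAP 10.2.12 and 10.2.13 restrict the duration and time-to analyses to subjects with sponsor-assessed CR/CRh and use the date it is first documented. Protocol 9.6.2 notes that investigators do not assess CRh.

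**The concern.** A programmer who follows the brackets and one who follows the main values will build different endpoints.

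- **Under the brackets**, CRh has essentially the count thresholds of full CR. It would then add only subjects who miss CR on a criterion other than counts, which defeats a category meant to capture partial hematologic recovery.
- **Under the protocol's ANC main value**, CRh is practically unattainable.

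No site assessment exists to check the derivation against. Once the marrow criterion is met, the coded count thresholds decide who is CRh and from which date. The justification for the current amendment says that the primary analysis report is already final, yet Appendix F still carries the faulty footnote. From the documents, a reader cannot tell which cut-off lies behind the CR+CRh results.

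**Working it through.** **Unit conversion.** 1 x 10^9/L = 1,000/µL, so v x 10^9/L = v x 1,000/µL.

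| Item | Main value (10^9/L) | Converted (per µL) | Printed bracket (per µL) | Bracket / converted |
|---|---|---|---|---|
| CR, ANC (both documents) | 1 | 1,000 | 1,000 | 1 |
| CR, platelets (both documents) | 100 | 100,000 | 100,000 | 1 |
| PD, peripheral blasts (both documents) | 10 | 10,000 | 10,000 | 1 |
| CRh, ANC (SAP 10.2.11 and 17.4) | 0.5 | 500 | 1,000 | 2 |
| CRh, platelets (all three places) | 50 | 50,000 | 100,000 | 2 |
| CRh, ANC (Protocol Appendix F) | 500 | 500,000 | 1,000 | 0.002 |

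The CR and PD rows convert correctly and every CRh row fails. With the same brackets in three separate places, this is not a fault of text extraction. The protocol's ANC main value is 500 / 0.5 = 1,000 times the SAP's. The brackets match the CR cut-offs in number only: CR uses ≥ and CRh uses >.

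**Who is affected.** Call counts intermediate when ANC is above 0.5 and platelets are above 50 x 10^9/L, but at least one is not above 1.0 or 100 respectively. All cases below assume less than 5% marrow blasts.

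Scheduled response assessments fall before Cycles 2 and 3, and then "Within 7 days prior to Day 1 of Cycle 5 and Day 1 of every 2nd cycle thereafter" (Protocol Table 4, footnotes w to y). At nominal 28-day cycles these are Days 29, 57, 113 and 169. The gaps are 28, 56 and 56 days. With the SAP 17.1.1 divisor, 28 / 30.4 = 0.92 months and 56 / 30.4 = 1.84 months.

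First CR/CRh day in illustrative courses (ANC/platelets in 10^9/L; the counts are invented to show the mechanism):

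| Course | SAP main values | Brackets | Protocol main values |
|---|---|---|---|
| 0.7/80 at all four visits, never CR | 29 | none | none |
| 0.7/80 at Cycle 2, CR at Cycle 3 | 29 | 57 | 57 |
| Below 0.5/50 at Cycle 2, 0.7/80 at Cycle 3, CR at Cycle 5 | 57 | 113 | 113 |
| CR at Cycle 2, then 0.7/80 | 29 | 29 | 29 |
| 1.5/150 at all visits, red-cell transfusion in the past week each time | 29 | 29 | none |
| 0.7/80 at Cycle 2, then 1.5/150 with transfusion | 29 | 57 | none |
| Never above 0.5 and 50 together | none | none | none |

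The transfused courses arise because CR requires "Independent of red cell transfusions for" at least a week, a condition the CRh text does not state.

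**Effect by group, main values against brackets.**

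1. Intermediate counts, never CR or bracket-level CRh: the subject's status changes. Each subject moves the rate by 1/66 = 1.5 points in Arm 1 or 1/33 = 3.0 points in Arm 2, and enters or leaves the time and duration analyses.
2. Intermediate counts first, CR or bracket-level CRh later: the rate is unchanged. Under the brackets the first date is later by a nominal 28 days (Cycle 2 to 3) or 56 days per later interval. Duration is shorter by the same amount if its end date is unchanged.
3. CR first: no change.

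**The case against.** The strongest reply accepts the text fault but calls it minor.

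- **The intended values are hardly in doubt.** Both SAP definitions print the same main values, and the SAP's other cut-points for these counts (the baseline categories in 8.2.1, the ANC subgroups in 11.1) are in 10^9/L. Protocol section 9 also hands over the methods: "The final statistical analysis methods will be documented in detail in the statistical analysis plan (SAP"). So the protocol's 500 should not drive the analysis. This stands as evidence of intent. It does not settle the brackets, because the SAP itself carries them.
- **No miscoding is shown.** That is true, and none is claimed. The need is to confirm which cut-off was used.
- **The count cut-off is not the only criterion.** Correct: the blast criterion applies too, and CR has further conditions. The count cut-off decides only among subjects who meet the marrow requirement.
- **The 28- and 56-day shifts are nominal.** Also correct. Marrow may be taken up to 7 days before Day 1, cycles may be delayed, extra marrows are allowed, and blood counts are drawn between marrow visits. The documents do not say how counts and marrow are paired. The shifts indicate scale and are not predictions.
- **No net effect on the arm comparison is shown.** That stands. The steps of 1.5 and 3.0 points would apply to any single reclassified subject.

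These points limit what can be said about consequences. They do not make the fault clerical, because the figures are the decision thresholds of an endpoint compared between arms.

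**Conclusion.** The concern holds. All three CRh definitions are internally contradictory. The brackets are twice the SAP's main values on both counts, and the protocol's ANC figure is a separate 1,000-fold discrepancy from the SAP. The SAP main values are very probably the intended ones; this is an inference from their repetition in the SAP and from the meaning of CRh, not something the documents state.

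The exposure is confined to the Phase 2 CR+CRh rate, the time to and duration of CR/CRh, and the descriptive Phase 1b CR/CRh endpoint. The per-subject steps assume the planned arm sizes of 66 and 33, and the date shifts assume nominal cycles and scheduled assessments. Because the documents do not give the number of subjects with intermediate counts, the direction and size of any effect on the arm comparison cannot be stated. ORR, sponsor-derived CR and the sample size are untouched. This should be fixed, but it does not threaten the primary analysis.

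**What to change.** Reconcile Protocol Appendix F, SAP 10.2.11 and SAP 17.4 to one definition built on the SAP's main values: less than 5% marrow blasts in an aspirate with spicules, ANC > 0.5 x 10^9/L (500/µL) and platelets > 50 x 10^9/L (50,000/µL). Check the derivation code and record the cut-off it applied. If that matches, a short documented confirmation is enough. If another cut-off was used, re-run the CR+CRh rate and the time and duration outputs, together with the Phase 1b CR/CRh summary.

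The cost is three text corrections and one code check. Re-analysis is needed only if the check fails.

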10.2.12. Duration of Sponsor Assessed CR and CRh

Duration of sponsor assessed CR and CRh is defined as time from first documented CR/CRh to documented morphologic relapse, PD, or death due to any cause, whichever occurs first. Subjects without morphologic relapse, PD, or death due to any cause will be censored at the date of the last response assessment.

The duration of response will be analyzed using the KM method. The 25th percentile, median and 75th percentile time (including two-sided 95% CI) will be summarized for each treatment arm. Only subjects with documented CR/CRh response as determined by sponsor assessment will be included in the analysis.

10.2.13. Time to Sponsor Assessed CR and CRh

Time to sponsor assessed CR and CRh is defined as time from first dose of study drug for Phase 1b subjects and the date of randomization for Phase 2 subjects to first documented CR/CRh.

Time to sponsor assessed CR and CRh will be analyzed using the summary statistics for each treatment arm. Only subjects with documented CR/CRh response as determined by sponsor assessment will be included in the analysis.

10.2.14. EORTC QLQ-C30 and EQ-5D-5L

For Phase 2, the analyses will address the mean differences by treatment arm on the EORTC QLQ-C30 scale and subscale scores and the treatment arm differences in the proportion of subjects who achieve minimal clinically important differences. The scoring for the EORTC QLQ-C30 and methods to address missing values will be accomplished according to directions provided by the instrument developer. The analyses of the EORTC QLQ-C30 will be based on all randomized subjects who completed the baseline assessment and had at least one post-baseline assessment with the EORTC QLQ-C30. The observed case method and the descriptive statistics will be used to summarize the observed scores and the change from baseline score by visit and the treatment arm for each domain of the QLQ-C30. In addition, frequency tables for categorized change from baseline scores (Improving, No Change, and Worsening) will be presented by treatment arm. A change of at least 10 points on the standardized domain scores will be required for it to be considered meaningful ([Osoba, 1998](#)).

For Phase 2, EQ-5D-5L will be scored according to the instrument guidance and analyzed accordingly. The EQ-5D-5L consists of 2 pages – the EQ-5D-5L descriptive system and the EQ Visual Analogue scale (EQ VAS). The descriptive system comprises of 5 dimensions: Mobility, Self-care, Usual Activities, Pain/Discomfort and Anxiety/Depression. Each dimension has 5 levels: no problems, slight problems, moderate problems, severe problems, and extreme problems. Responses from the 5 dimensions are coded so that a ‘1’ indicates no problem on that dimension, and ‘5’ indicates the most serious problem. The responses for the five dimensions can be combined in a five-digit number describing the respondent’s health state. For instance, a state of 11111 indicates no problem with any of the 5 dimensions, but a state of 55555 indicates the most difficulty on all 5. Missing and un-interpretable values (e.g. two responses are given for a single dimension) which are not recoverable through queries will be coded as ‘9’. These health states will be converted to a single index value using the crosswalk link function based on the existing value sets derived based on United Kingdom time trade-off (TTO) valuation techniques.

EQ VAS is a respondent's self-rated today's health scale which is recorded on a 20 cm vertical, visual analogue scale with endpoints labeled "the best health you can imagine" and "the worst health you can imagine". The scale is numbered from 0 to 100 with 0 corresponding to the worst imaginable health state and 100 corresponding to the best imaginable health state.

The analyses of the EQ-5D-5L will be based on all randomized subjects who completed the baseline assessment and had at least one post-baseline assessment with the EQ-5D-5L. The observed case method and the describable statistics will be used to summary the EQ VAS and index values and the change from baseline by visit and the treatment arm.

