For **HRQoL** data, analyses will address the mean differences by treatment group on the EORTC QLQ-C30 scale and subscale scores and the treatment group differences in the proportion of subjects who achieve minimal clinically important differences. EQ-5D-5L will be scored according to the instrument guidance and analyzed accordingly.

Overall survival and one year survival rates will be analyzed using Kaplan-Meier method, and the treatment comparison will be conducted using log-rank test.

The other secondary endpoints include complete remission rate, best overall objective response rate, rate of hematologic improvement (HI), the sponsor assessed CR/CRh (based on laboratory dataset) and duration of CR/CRh. These endpoints will be analyzed using the statistical methods mentioned above or other statistical methods as appropriate. As noted, CRh is not available from the investigator assessment. As a result, the analyses on CR/CRh will be based on the sponsor derived assessment.

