3.2. Secondary Objectives

For the Phase 1b Dose-finding Stage:

[figure not shown]
- To assess the preliminary efficacy of the combination treatments of oral AG-120 when administered with SC azacitidine and oral AG-221 when administered with SC azacitidine in subjects with newly diagnosed AML with an IDH1 or an IDH2 mutation, respectively, who are not candidates to receive intensive IC.

For the Phase 1b AG-120 Expansion Stage:

- To assess the preliminary efficacy of the combination treatments of oral AG-120 when administered with SC azacitidine in subjects with newly diagnosed AML with an IDH1 mutation, who are not candidates to receive intensive IC.
- To characterize the pharmacokinetics (PK) of oral AG-120 when administered with SC azacitidine.

For the Phase 2 AG-221 Randomized Stage:

- To evaluate the safety of oral AG-221 when administered with SC azacitidine.
- To characterize the PK of oral AG-221 when administered with SC azacitidine.
- To evaluate the effect of oral AG-221 when administered with SC azacitidine versus SC azacitidine alone on health-related quality-of-life (HRQoL) outcomes.

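### The Phase 2 HRQoL objective compares the arms, but SAP 10.2.14 specifies only observed-case descriptive summaries and names no baseline-adjusted between-arm estimate

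*SAP*

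**What the plan says.** The objective is comparative. SAP 3.2 lists it as "To evaluate the effect of oral AG-221 when administered with SC azacitidine versus SC azacitidine alone on health-related quality-of-life (HRQoL) outcomes", and the protocol's Table 1 carries the same objective. Protocol 9.6.2 says that "analyses will address the mean differences by treatment group on the EORTC QLQ-C30 scale and subscale scores", together with arm differences in the proportion reaching a minimal clinically important difference. SAP 10.2.14 repeats the commitment: "the analyses will address the mean differences by treatment arm on the EORTC QLQ-C30 scale and subscale scores".

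The method that SAP 10.2.14 then gives for the QLQ-C30 is descriptive: "The observed case method and the descriptive statistics will be used to summarize the observed scores and the change from baseline score by visit", by treatment arm. The analysis set is "all randomized subjects who completed the baseline assessment and had at least one post-baseline assessment with the EORTC QLQ-C30". In addition, "frequency tables for categorized change from baseline scores (Improving, No Change, and Worsening) will be presented by treatment arm", with the threshold "A change of at least 10 points on the standardized domain scores will be required for it to be considered meaningful". For the EQ-5D-5L, observed-case descriptive statistics "will be used to summary the EQ VAS and index values and the change from baseline by visit and the treatment arm".

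The section names no model, test, principal domain or principal time point. It does not say how death or treatment discontinuation is handled.

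On collection, the Table of Events (protocol Table 4, SAP 17.3) schedules both questionnaires on Day 1 of each cycle and at end of treatment (EOT), with a dash under follow-up. Protocol 6.2.3 includes them at EOT. Protocol 6.3 does not list them among the follow-up assessments.

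**The concern.** A comparative objective needs a defined between-arm quantity and a way to estimate it. Here the stated method stops at a table of means for each arm at each visit. Other comparative secondary endpoints in SAP 10.2 have a named method: log-rank and Cox for event-free and overall survival, chi-square or Fisher tests for rates, and a difference with CI for one-year survival. HRQoL has none.

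The by-visit means also describe a shrinking, selected group. After Cycle 1, a Day 1 score exists only for a subject who is still on treatment and completed the form. If subjects with poorer scores leave sooner, and at different rates in the two arms, the two observed means at a late cycle describe differently selected groups. The plan assumes 50% against 30% response, so unequal time on treatment is plausible. The control arm starts with only 33 subjects.

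At stake is the reading of one secondary objective: a comparison that may be distorted by dropout and is less precise than the collected data allow.

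**Working it through.** **The plan's own figures.** The documents give no HRQoL sample size, SD, correlation, effect size or dropout rate, so there is no HRQoL figure to reproduce. The one power figure, 75% for ORR of 50% against 30% with 66 and 33 subjects at two-sided 0.2, does reproduce (73.9% by the pooled normal formula, 75.3% by exact enumeration of the uncorrected chi-square). It does not bear on this point. Everything below is illustration on assumed inputs, apart from the 66:33 allocation and the 10-point threshold. In the simulations, the true value is the difference at the sixth post-baseline visit if every subject had been measured.

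**1. No true difference.** Assumed: mean 50 and SD 22 in both arms at every visit, autoregressive scores with lag-1 correlation 0.8, and log-odds of dropout falling by 0.4 per SD of the previous score.
- With 52%, 34% and 22% retained, the observed raw means are 52.6, 54.3 and 55.4.
- Taking 52% as the AG-221 arm and 34% or 22% as control, the spurious raw difference is 54.3 − 52.6 = 1.7 or 55.4 − 52.6 = 2.8 points, in favour of the arm with more dropout.
- In the same runs, the mean change from baseline differs by about 0.2 and 0.7 points in the opposite direction. Selection acts on the baseline and intermediate scores more directly than on the final one, so those who remain regress towards the mean.
- Over other assumed correlations and dropout slopes, the raw shift was about 1 to 5 points and the change-score shift about 0.2 to 1.7 points the other way.

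**2. A true difference of about 6 points.** Assumed: starting mean 55, between-subject SD 14, residual SD 12, and individual slopes with SD 4 around a mean of 0 (AG-221) or −1 (control) per visit. Over six visits the difference is 6 × 1 = 6. The table compares the observed-case difference in change with an estimate valid under missing at random (each visit regressed on all earlier scores within arm).

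| Log-odds of dropout per 20-point lower score | Dropout per visit at score 55, AG-221 / control | Retained | True | Observed-case change | Missing-at-random estimate |
|---|---|---|---|---|---|
| 0 | 5% / 10% | 73% / 53% | 6.00 | 6.00 | 6.09 |
| 0.5 | 5% / 10% | 71% / 49% | 6.17 | 4.27 | 6.10 |
| 1.0 | 5% / 10% | 65% / 43% | 5.95 | 3.32 | 6.14 |
| 1.0 | 5% / 15% | 65% / 32% | 6.10 | 1.49 | 5.96 |

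Unequal dropout alone does no harm (first row). Dropout that is both unequal and score-dependent shrinks the difference to 1.5 to 4.3.

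**3. Precision.** With common SD σ and baseline correlation ρ, the variance of an unadjusted change is 2σ²(1 − ρ) and that of a baseline-adjusted score is σ²(1 − ρ²). The ratio is (1 + ρ)/2.
- ρ = 0.4 gives 0.70, a 30% reduction. ρ = 0.6 gives 0.80, a 20% reduction.
- With 66 and 33 subjects and nothing missing, √(1/66 + 1/33) = 0.2132. At SD 20 and ρ = 0.5, the standard error is 20 × 0.2132 = 4.26 for change and 4.26 × √0.75 = 3.69 after adjustment.

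**The case against.** Four points can be put for the plan.

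- **Baseline is used.** A reader might infer from the observed-case method that baseline is ignored. It is not: the SAP summarises change from baseline for both instruments, categorises change at 10 points and requires a baseline form. What is missing is baseline as a covariate in a between-arm estimate.
- **Subjects who stop are not wholly lost.** A reader might infer that nothing is collected once treatment ends. Each subject who stops is due one EOT questionnaire and can enter the analysis set through it. That stands, but it is one form at a varying time, and the SAP does not say how it enters the by-visit comparison.
- **General defaults exist.** SAP 5.1 and the opening of SAP 10 call for two-sided 95% CIs, the latter for intended point estimates. So it goes too far to say that no interval would be reported. The default still needs an estimator to attach to, and for HRQoL none is defined.
- **The stakes are modest.** HRQoL is one of many secondary endpoints in a 99-subject Phase 2 with no HRQoL power claim. In the null example, 0.52 × 66 ≈ 34 and 0.34 × 33 ≈ 11 subjects remain. The standard error of a raw difference is then 22 × √(1/34 + 1/11) ≈ 7.6, so a shift of 1.7 is about 0.2 standard errors. That is fair, and it limits the urgency.

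It is also true that a repeated-measures model assumes data are missing at random and, left unqualified, implies scores after death. The fix has to address both.

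**Conclusion.** The point holds as a gap between a comparative objective and a purely descriptive method. By-visit summaries of subjects still on treatment are open to bias when dropout depends on earlier scores and differs by arm. A named model on data already collected would remove that bias under missing at random and improve precision.

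The documents do not fix the size or the direction. A reader might infer that the method works against AG-221 by a few points. That follows only for raw means, only with no true difference, and only if control loses more subjects. The change score moves the other way in the same scenario, and with an assumed true benefit it shrinks. The SAP lists raw scores and change side by side without ranking them, so the two can disagree when nothing differs. The spurious shifts and the shrinkage seen here are all below the SAP's 10-point threshold for a meaningful change. The SAP text should be amended, but the primary endpoint is not touched.

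**What to change.** Add to SAP 10.2.14:

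- **Model.** A mixed model for repeated measures on change from baseline, with baseline score, AML type (the randomisation stratum), visit, arm and arm-by-visit. Report the adjusted arm difference with 95% CI at a named visit for named domains. Choose a visit at which the control arm is still expected to contribute enough subjects.
- **Assumptions.** State that the model assumes data are missing at random, that estimates after death are not interpreted, and how the EOT form is used.
- **Sensitivity analysis.** One simple missing-not-at-random analysis, for example shifting predicted scores after discontinuation by fixed amounts up to the SAP's 10 points.
- **Supportive output.** Keep the observed-case and frequency tables as supportive, and report questionnaire completion rates by visit and arm.

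The cost is a few lines of SAP text and modest programming, with no new data. The price is the stated missing-at-random assumption. If HRQoL results by arm have already been seen, label the model as added afterwards.
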